#### 4.9.2.2 Sensitivity Analysis of Primary Endpoint

The following sensitivity analyses of the primary endpoint will be conducted to assess the robustness of the primary analysis result.

##### **Sensitivity Analysis 1:**

The primary analysis with ANCOVA model for percent change in fasting TG from Baseline to Month 6 will be repeated in the PPS.

### **Sensitivity Analysis 2 - Completer Set:**

The primary efficacy analysis with ANCOVA model for percent change in fasting TG from Baseline to Month 6 will be repeated in a subset of patients in the FAS with no missing TG value at baseline and Month 6.

### **Sensitivity Analysis 3:**

A nonparametric Wilcoxon rank-sum test will be performed on the percent change in TG from baseline to Month 6 based on FAS. Missing data will be handled using the same multiple imputation method as the primary analysis. The estimates from the fitted model for each of the 100 imputed datasets will be combined to provide an overall Hodges-Lehmann estimator of the location shift and corresponding 95% CI between olezarsen 80 mg group and placebo group. The same approach will be used for comparison between olezarsen 50 mg group and placebo group.

The example SAS code can be found below:

```
/* ***** */
/* Note: */
/* pchg = percent change of TG from baseline to Month 6 */
/* impute = the iteration number in the multiple mutation */
/* trtpn = treatment group: 0=placebo, 1=olezarsen 80 mg */
/* ***** */
proc nparlway data= TGIM h1 alpha=0.05;
  class trtpn;
  var pchg;
  by impute;
run;
```

### **Sensitivity Analysis 4 - Tipping point analysis using FAS:**

An additional sensitivity analysis using the 2-dimensional tipping-point approach will be conducted in the FAS to assess the impact of missing data on the result of the primary analysis. The sensitivity analysis will be conducted as follows using the imputed data based on the primary imputation approach as described in Section 4.9.1.4 in the SAP:

1. For the placebo group, a positive constant shift ( $\delta_c$ , %) will be added to or subtracted from the percent change of imputed TG values at the primary time point. The shift will gradually increase.
2. For each value of the placebo shift parameter, a positive constant shift ( $\delta_t$ , %) will be added to or subtracted from the percent change of imputed TG values at the primary time point in the active treatment groups. The shift will be increased in a repeated process until the treatment effect is no longer significant at 0.05 level in step 5 below.
3. For each of the 100 imputed datasets, the same ANCOVA model as described for the primary analysis of the primary endpoint will be fitted to estimate treatment differences and standard errors.
4. The 100 sets of estimates will be combined with SAS PROC MIANALYZE as described in Section 4.9.1.4 in the SAP.
5. Steps 1 to 4 will be repeated with different values of the shift parameters until the tipping points are reached.

Values of  $\delta_c$  and  $\delta_t$  will be determined post-hoc in order to define reasonable increments.

### **Sensitivity Analysis 5 - Exploring the robustness of the primary analysis (FAS):**

A few sensitivity analyses using controlled imputations (pattern mixture models (PMM)) with ANCOVA will be conducted in the FAS to assess the impact of alternative missing data assumptions on the robustness of the primary analysis results.

- Patients treated with olezarsen who discontinue the treatment due to AE (i.e., informative missing), their missing TG data after the last “observed value will be multiply imputed using the copy increment from reference (CIR) approach (Carpenter et al. 2013) based on the estimates from of the placebo patients. The assumption is when a patient discontinues treatment due to informative missing, they continue to take advantage of their previous therapy, but from discontinuation onwards he/she would progress in the same way as the patients in the placebo group (i.e., parallel to the profile for the placebo group). For patients who discontinue due to other reasons and all patients from the placebo group, their missing data will be treated as non-informative missing, and data will be multiply imputed based on the distribution of their own arm. The reason for this is that it is assumed those patients would have proceeded in the future, in a comparable way to similar patients (with similar baseline and covariates) in their own treatment who did remain in the trial. The analysis will be conducted in the FAS. Baseline and post-baseline fasting TG will be natural log-transformed before the imputation process, the data will be back transformed to create the imputed data set after the imputation.
- All patients treated with olezarsen who discontinue the treatment will have missing TG values after the last “observed value multiply using the CIR approach based on the estimates from the placebo patients. Missing TG for placebo patients will be imputed using the MI method as the primary analysis.

Baseline and post-baseline fasting TG will be natural log-transformed before the imputation process, the data will be back transformed to create the imputed data set after the imputation.

### **Sensitivity Analysis 6 - ANCOVA model using log-transformed data (FAS)**

The percent change from Baseline to Month 6 in fasting TG between each olezarsen treatment group (olezarsen 80 mg, olezarsen 50 mg) vs. pooled placebo will be compared using ANCOVA model with  $\log(y/x)$  as dependent variable, where y is the value of fasting TG at Month 6, x is the baseline value of fasting TG; treatment group as factor and nature log-transformed baseline fasting TG as a covariate. The model will provide an estimate of log post-baseline to baseline ratio for each treatment group as well as the ratios relative to the pooled placebo group and the corresponding SEM. The log post-baseline to baseline ratios will be converted back to the original ratio scale. The percent change from baseline for each treatment group will then be calculated based on the estimated ratio as  $100\% * (\text{ratio} - 1)$ . Similarly, the estimated upper and lower CIs for the ratio can be calculated as  $100\% * (\text{CI} - 1)$ . Patients with missing fasting TG value at Month 6 will have fasting TG value multiply imputed using the multiple imputation methods described in Section 4.9.1.4 in the SAP.

#### *4.9.3 Secondary Efficacy Variables*

To control the type I error, a hierarchical ranking strategy will be employed with the sequence of endpoints defined as in Section 4.9.1.5.

#### 4.9.3.1 *Percent Change in Fasting TG From Baseline at Month 12*

The percent change in fasting TG from Baseline to Month 12 (average of Week 51 and Week 53) in the FAS will be analyzed in the same way as for the primary endpoint.

The same set of sensitivity analyses (sensitivity analysis 1 to sensitivity analysis 6) and subgroup analysis as for the primary endpoint will be conducted for the percent change in fasting TG from Baseline to Month 12.

#### 4.9.3.2 *Proportion of Patients Who Achieve Fasting TG < 150 mg/dL at Month 6 and at Month 12 in the Subgroup of Patients with Baseline fasting TG < 500 mg/dL*

The proportion of patients who achieve fasting TG < 150 mg/dL (1.69 mmol/L) at Month 6 and Month 12 in the subset of FAS with Baseline fasting TG < 500 mg/dL (5.65 mmol/L) will be compared between each olezarsen treatment group and placebo group using a logistic regression model with the treatment group as the factor, and natural log-transformed baseline fasting TG as a covariate. Missing TG values will be imputed using the same multiple imputation method as the primary analysis of the primary endpoint. For each of the 100 imputed datasets obtained from Section 4.9.1.4, the logistic regression model described above will be fitted and the estimates from each of 100 fitted model will be combined to provide an overall odds ratio with corresponding CIs and p-value.

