### 2.3.4 Clinical Experience

Detailed information concerning the clinical studies conducted with ISIS 678354 (olezarsen) can be found in the Investigator's Brochure. In addition, the results of the ISIS 678354-CS1 Phase 1 study, and Phase 2 study are provided in the respective publications ([Alexander et al. 2019](#);

[Tardif et al. 2022](#)). A short summary of the Phase 2 study conducted with ISIS 678354 is included below.

The Phase 2 study was a multicenter, randomized, double-blind, placebo-controlled, dose-ranging study. A total of 114 patients with established ASCVD, or being at risk for ASCVD, with fasting TG levels of  $\geq 200$  mg/dL and  $\leq 500$  mg/dL, and on standard-of-care preventative therapy for their known ASCVD risk factors were treated with subcutaneous (SC) injections of ISIS 678354 or matching placebo in the range of dosing equivalent to monthly drug exposure of 10 mg to 50 mg, for 6 to 12 months. Significant reductions in fasting TG levels from Baseline to the primary analysis time point at Month 6 were observed in all ISIS 678354-treated groups compared to placebo. The highest dose group (50 mg every 4 weeks) achieved mean 62% reduction from Baseline in fasting TG levels compared to placebo, associated with mean 74% reduction from Baseline in apoC-III, 57% of reduction in VLDL, and 20% reduction in non-HDL-C levels. The proportion of patients achieving normal fasting TG levels  $< 150$  mg/dL showed a significant, dose-dependent increase in all ISIS 678354 treated groups with over 90% (20/22) patients treated with the highest dose of 50 mg Q4W vs. only 4.2% (1/24) patients treated with placebo achieving this threshold.

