### 10.2 Sample Size Considerations

With 33 patients in each olezarsen treatment group and 22 in the pooled placebo group, there would be an approximately 80% power to detect a 60% difference between each olezarsen treatment group and pooled placebo group at an alpha level of 0.05 (two-sided), assuming 60% reduction in the olezarsen treatment patients, no change in the placebo patients, and a common SD of approximately 73%. It is estimated that dropout rate is approximately 20%.

Approximately 152 patients will be enrolled in this trial to account for potential early dropouts and to facilitate general safety evaluations.

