#### 4.9.1.5 Multiple Comparisons/Multiplicity

The multiplicity will be controlled by using a hierarchical ranking strategy in the following testing sequence. All tests will be conducted at a two-sided alpha level of 0.05. For the primary endpoint family, the 2 treatment arms will be compared against placebo using the hierarchical testing procedure, in which the olezarsen 80 mg treatment group will be compared to the placebo at the 2-sided alpha level of 0.05, if the comparison is statistically significant ( $p < 0.05$ ), then the olezarsen 50 mg treatment group is compared against the placebo at the alpha level of 0.05. If the comparison of the olezarsen 80 mg treatment group to placebo group is not statistically significant, then the comparison of the olezarsen 50 mg treatment group against placebo and all

secondary endpoints will be considered exploratory. The order of the testing on the secondary endpoints is outlined below. The endpoint ranked as first will be tested and the difference will be declared statistically significant if the p value is less than 0.05. In case that the difference for the first endpoint is statistically significant, the endpoint ranked as second will be tested, and the difference will be declared statistically significant if the p-value is less than 0.05. The testing will continue as long as the previously ranked endpoint is statistically significant. If the secondary endpoints are not evaluated as a part of the hierarchical testing procedure due to previously ranked endpoint was not statistically significant, the statistical tests will be reported and interpreted in a descriptive manner.

1. Primary endpoints family:

- Primary endpoint: Comparison of percent changes in fasting TG from Baseline to Month 6 between olezarsen 80 mg treatment group and placebo in the FAS
- Primary endpoint (not co-primary endpoint): Comparison of percent changes in fasting TG from Baseline to Month 6 between olezarsen 50 mg treatment group and placebo in the FAS

2. Secondary endpoints will be tested in the FAS according to the following sequence:

- Comparison of percent change in fasting TG from Baseline to Month 12 between olezarsen 80 mg and placebo group
- Comparison of percent change in fasting TG from Baseline to Month 12 between olezarsen 50 mg and placebo group
- Comparison of percent change in fasting apoC-III from Baseline to Month 6 between olezarsen 80 mg and placebo group

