#### 4.9.3.3 *Percent Change in Fasting ApoC-III, VLDL-C, Remnant Cholesterol, Non-HDL-C, HDL-C, TC, ApoB, LDL-C, and ApoA-1 From Baseline at Month 6 and at Month 12*

The percent change in fasting apoC-III, VLDL-C, remnant cholesterol, non-HDL-C, HDL-C, TC, apoB, LDL-C, and apoA-1 from Baseline to Months 6 and Month 12 in the FAS will be analyzed in the way similar to that for the primary endpoint using an ANCOVA model with percent change from Baseline to Month 6 or Month 12 in fasting value as the dependent variable, treatment group (olezarsen 80 mg, olezarsen 50 mg, or Placebo) and baseline stratification factor as factors, and natural log-transformed baseline value as a covariate.

The sensitivity analyses using the imputation models as described in sensitivity analysis 3 and 5 for the primary endpoint will be conducted.

4.9.3.4 *Proportion of Patients Who Achieve Fasting TG < 500 mg/dL at Month 6 and at Month 12 in the Subgroup of Patients with Baseline fasting TG  $\geq$  500 mg/dL*

The proportion of patients who achieve fasting TG < 500 mg/dL at Month 6 and Month 12 will be analyzed in the same way as the proportion of patients who achieve fasting TG < 150 mg/dL. It will be conducted in the subset of FAS with baseline fasting TG  $\geq$  500 mg/dL. Tipping point analysis will not be performed.

4.9.3.5 *Adjudicated Acute Pancreatitis Event Rate During the Treatment Period in the FAS*

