## **4.12 Determination of Sample Size**

With 33 patients in each olezarsen treatment group and 22 in the placebo group, there would be an approximately 80% power to detect a 60% difference between each olezarsen treatment group and placebo group at an alpha level of 0.05 (two-sided), assuming 60% reduction in the olezarsen treatment patients, no change in the placebo patients, and a common SD of approximately 73%.

Approximately 152 patients will be enrolled in this trial to account for potential early dropouts.

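### TG < 150 mg/dL is tested by ordinary logistic regression with no fallback for an empty placebo cell, so a very large effect could fail the test and end the confirmatory sequence

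*Combined protocol and SAP*

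**What the plan says.** SAP 4.9.3.2 covers patients with baseline TG < 500 mg/dL. The proportion reaching TG < 150 mg/dL at Months 6 and 12 "will be compared between each olezarsen treatment group and placebo group using a logistic regression model with the treatment group as the factor", with natural-log baseline TG as covariate. The model is fitted in each of 100 imputed datasets, and the fitted estimates are combined into one odds ratio, CI and p-value. No code or test is named. For the primary endpoint, SAP 4.9.2.1 pools estimates and standard errors with PROC MIANALYZE.

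SAP 4.9.3.4 carries the method over to TG < 500 mg/dL in patients with baseline TG ≥ 500 mg/dL: that endpoint "will be analyzed in the same way as the proportion of patients who achieve fasting TG < 150 mg/dL".

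The two sensitivity analyses in 4.9.3.2 (non-responder imputation and a tipping point) address missing data and do not replace the confirmatory p-value. A rule for too few events exists only for pancreatitis (4.9.3.5: Clopper-Pearson interval and Fisher's exact p).

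On the sequence, SAP 4.9.1.5 states: "The testing will continue as long as the previously ranked endpoint is statistically significant". Tests not reached this way are reported descriptively.

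The only prior evidence on this endpoint is in Protocol 2.3.4: "over 90% (20/22) patients treated with the highest dose of 50 mg Q4W vs. only 4.2% (1/24) patients treated with placebo" reached TG < 150 mg/dL in Phase 2.

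**The concern.** Maximum-likelihood logistic regression has no finite treatment estimate when one arm has no responders or only responders (separation). The iterations drift outward, the standard error grows faster than the estimate, and the Wald statistic shrinks towards zero. The test then fails because the effect is very large.

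Phase 2 was one placebo responder away from this. Here the test is a gate. If it fails for 80 mg at Month 6, every later comparison loses confirmatory status, including VLDL-C, non-HDL-C, HDL-C, remnant cholesterol, apoB and LDL-C. The same model recurs at three more steps (80 mg Month 12, then 50 mg Months 6 and 12). Switching method after seeing an empty cell would be a data-driven change to a gatekeeping test.

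**Working it through.** **The plan's own figure.** No power is stated for this endpoint. The stated power is for the primary comparison: "With 33 patients in each olezarsen treatment group and 22 in the placebo group, there would be an approximately 80% power", for a 60-point difference with "a common SD of approximately 73"%. SE = 73 × √(1/33 + 1/22) = 20.09. Power = Φ(60/20.09 − 1.96) = Φ(1.03) ≈ 84.8% (83.4% with the t distribution). The stated 80% is therefore conservative, and this has no bearing on the responder test.

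**Position in the sequence.** Counting SAP 4.9.1.5:
- TG Month 12: tests 1-2.
- apoC-III: tests 3-6.
- TG < 150, 80 mg, Months 6 and 12: tests 7-8.
- TG < 150, 50 mg, Months 6 and 12: tests 17-18.
- TG < 500: tests 43-46.
- Pancreatitis: tests 47-48.

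After test 7 there remain 48 − 7 = 41.

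**Arm sizes.** 152 patients split 1:1, then 3:1, give 57 on 80 mg, 57 on 50 mg and 38 on pooled placebo. The share with baseline TG < 500 mg/dL is not documented, so it is varied.

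**Chance of separation at the Phase 2 rates.** P(no placebo responder) = (23/24)^n. P(all active respond) = (20/22)^m. P(either) = 1 − (1 − first)(1 − second).

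| Share with TG < 500 | n placebo / m 80 mg | No placebo responder | All active respond | Either |
|---|---|---|---|---|
| 100% | 38 / 57 | 20% | 0.4% | 20% |
| 90% | 34 / 51 | 24% | 0.8% | 24% |
| 75% | 28 / 43 | 30% | 1.7% | 32% |
| 50% | 19 / 28 | 45% | 6.9% | 48% |

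Other assumed rates, for shares of 100% to 50%:
- Placebo 10%, active 91%: 2% to 20%.
- Placebo 15%, active 91%: 1% to 11%.
- Phase 2 placebo rate, 80 mg at 97%: 34% to 68%.

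**What the test returns (two-arm fits with log baseline).**

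| Data | Ordinary Wald p, by iterations allowed (8 to 25) | Firth p |
|---|---|---|
| 0/38 vs 52/57 | 0.40 to 1.00 | 0.00003 |
| 0/29 vs 39/43 | 0.53 to 1.00 | 0.00003 |
| 0/19 vs 26/29 | 0.62 to 1.00 | 0.0003 |
| 1/29 vs 39/43 | < 0.0001 (log OR 5.61, SE 1.1) | < 0.0001 (log OR 4.96) |

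**Why pooling does not rescue it.** Rubin's total variance is T = W + (1 + 1/100)B, with W the mean squared SE and B the between-dataset variance. Suppose 99 datasets look like 1/29 vs 39/43 (5.61, SE 1.1) and one is separated and stopped at 10 iterations (13.51, SE 50.0).
- W = (99 × 1.21 + 2500)/100 = 26.2.
- B = 0.01 × (13.51 − 5.61)² = 0.62.
- T = 26.8 and √T = 5.18.
- The pooled estimate is 5.69, so z = 1.10, not significant.

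With stopping at 8 iterations (11.51, SE 18.4), three separated datasets suffice: W = 11.33, B = 1.02, T = 12.36, estimate 5.79, z = 1.65.

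**Simulation of the pooled test.** Each cell has 300 trials, 20 imputations under the SAP's jump-to-reference fallback, and 0, 10 or 20% missing data. TG follows an assumed lognormal model calibrated to the Phase 2 rates. Moving the entry floor from 200 to 150 mg/dL gives a placebo rate of 8-15% in that type of model.

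| Placebo / 80 mg | Non-significant, floor 200 | Non-significant, floor 150 |
|---|---|---|
| 38 / 57 | 23-27% | 3-5% |
| 29 / 43 | 30-36% | 7-10% |
| 19 / 29 | 46-52% | 17-32% |

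With missing data, most failing trials had only some imputed datasets separated. For example, at 38/57, floor 200 and 10% missing, 26.3% of trials failed, while only 6.3% had every dataset separated.

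In complete-data simulations of the three-arm model at 4.2% vs 91% (300 trials per cell; 38, 30 or 20 placebo patients), the ordinary Wald test failed in 15%, 27% and 39%. Firth failed in none. Monte Carlo SE is about √(0.27 × 0.73/300) = 2.6 points.

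**The case against.** The strongest reply is that the Phase 2 rate comes from a different population. Phase 2 enrolled TG of 200-500 mg/dL, whereas the non-severe group here enters from 150 mg/dL. Baseline is an average of Qualification and Day 1 values, so some patients can start close to the 150 mg/dL threshold and cross it on placebo. The rate itself is 1 of 24, with an exact 95% CI of about 0.1% to 21%. This stands. It lowers the likely risk and makes any single figure unreliable.

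It is also fair that the Wald test is inferred. The SAP names no procedure for this model, and Firth estimation is still logistic regression, so specifying it is close to a clarification. The SAP Introduction allows updates. But pooling estimates into a p-value is a Wald-type construction, and silence leaves the choice until after the data are seen.

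A reader might infer that separation is likely. The documents do not support that: at the Phase 2 rates the chance stays below one half for subgroup shares of 50% or more. A reader might also expect p close to 1. The value depends on the software's stopping rule (0.40 to 1.00 in the examples), although it was non-significant in every separated example.

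The small TG ≥ 500 mg/dL subset may look more alarming still. Its size is not documented, so no failure rate can be given. Its tests rank 43-46, with only the two pancreatitis comparisons after them.

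**Conclusion.** The gap is real and should be fixed; it is a cheap improvement. The planned test for TG < 150 mg/dL can fail because the effect is too large, and the SAP has no prespecified way out.

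The chance at one test is about 20-48% at the Phase 2 rates, for subgroup shares of 100-50%. It is about 3-32% if the lower entry floor raises the placebo rate as in the assumed model. A response to 80 mg above the Phase 2 50 mg rate would raise it again. These ranges rest on the subgroup share, baseline TG distribution, TG variability and amount of missing data, none of which the documents give. The pooled simulation used the jump-to-reference fallback with 20 imputations, not the retrieved-dropout method or the full 100.

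The consequence is loss of confirmatory status for up to 41 secondary comparisons, which would still be reported descriptively. It would be wrong to infer that the main result is at risk: Type I error is not inflated, and both primary tests and the first six secondary tests come before this step.

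**What to change.** In SAP 4.9.3.2, and by reference in 4.9.3.4, prespecify Firth penalised logistic regression (treatment group plus log baseline TG) in each of the 100 imputed datasets. Pool the Firth estimates and standard errors by Rubin's rules for the hierarchical p-value. Report the ordinary logistic odds ratio as descriptive. Make the change before unblinding.

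The same fit is preferable to an exact test for TG < 500 mg/dL. An exact test would drop the baseline covariate and would need its own rule for combining p-values over imputations.

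The cost is one option (FIRTH in PROC LOGISTIC) and a sentence of SAP text, with no new data. The downside is some shrinkage of the odds ratio. In the 1/29 vs 39/43 example the log odds ratio falls from 5.61 to 4.96, about 12% on the log scale ((5.61 − 4.96)/5.61). The Firth runs above used complete data. A short check of the pooled version on dummy data would be sensible before the text is final.
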